## **5.9 Radiation**

All patients will receive daily radiotherapy with intensity-modulated radiotherapy (IMRT) delivered at DFCl. The prescribed dose will be 70 Gy (gray, SI unit of absorbed radiation) to the primary and nodal gross tumor volume, given in 2 Gy daily fractions for a total of 35 fractions. Other target volumes will be treated to 63 Gy and 56 Gy using differential dosing, as described below. There will be no planned cone downs or field changes. Treatment will be given 5 days per week for 7 weeks; treatment will not be planned to be delivered on Saturday, Sunday or major holidays, as per standard practice. Radiotherapy will be administered according to the general guidelines below.

- **Volume Definitions**-Volumes for all structures must be contoured on each relevant CT slice.

**Gross tumor volume (GTV)** consists of tumor at the primary site and gross nodal disease. The volumes will be defined based on imaging studies (CT and/or PET), in conjunction with information from clinical examination.

**High risk clinical target volume (CTV1)** includes volumes of potential tumor extension (adjacent to the primary or nodal GTV) and clinically/radiographically uninvolved nodal volumes at highest risk for microscopic involvement. The required anatomic margin around the GTV and gross nodal disease will be determined on a case-by-case basis by the treating radiation oncologist, limited by appropriate anatomic constraints. For gross nodal disease, CTV1 will include the nodal station where that node is located. In addition, the high risk clinical target volume may also include the complete anatomic nodal levels immediately adjacent to nodal regions that have gross disease.

**Low risk clinical target volume (CTV2)** includes lymph node regions at lesser risk for nodal involvement.

**Planning target volume (PTV)** incorporates a margin that accounts for daily set up variation. The planning target volume will be a 0.5 cm expansion of the gross and clinical target volumes. Modification of PTV is allowed at the discretion of the treating radiation oncologist for sparing of normal tissues, or if it is needed to facilitate the planning process, e.g. if the PTV overlaps a critical structure that must be spared. Each CTV will have an individual PTV designed for set-up uncertainty.

- **Avoidance Structures**–The following normal tissue structures will be defined and delineated on all appropriate CT slices:

- (a) Spinal cord, brainstem
- (b) Expanded Spinal Cord (7 mm expansion around spinal cord)
- (c) Right and left parotid glands
- (d) Larynx
- (e) Oral cavity

- **Avoidance Structures**–For cases in which the nasopharynx or base of skull is the primary target, the following avoidance structures will be added:

- (a) Inner ear
- (b) Optic nerves
- (c) Optic chiasm
- (d) Expanded optic nerve and chiasm (2 mm expansion around these structures)
- (e) Eyes
- (f) Brain

- **Target Dose Prescriptions.** The three target volumes are described in Section 5.8. All will be treated daily over the course of 35 fractions. The prescription point is at isocenter. To accommodate for tissue heterogeneity, density corrections are required, and will be applied to all plans, unless contraindicated, for example, by significant amounts of scatter on the planning CT scan. Doses will be planned as follows:

- (a) **GTV** will be treated to a total dose of 70 Gy in 2.0 Gy fractions.
- (b) **CTV1** will be treated to a total dose of 63 Gy in 1.8 Gy fractions.
- (c) **CTV2** will be treated to a total dose of 56 Gy in 1.6 Gy fractions.
- **PTV coverage:** No more than 20% of the PTV may receive > 110 % of the prescription dose. No more than 3% of the PTV may receive < 95% of the prescription dose. No more than 1cc of tissue outside the PTV may receive > 110% of the prescription dose.
- **Normal Tissue Doses**–The following normal tissue limits are recommended:
  - (a) **Parotid Glands:** Mean dose of 26 Gy or less.
  - (b) **Larynx:** Dose to the larynx should be limited to 50 Gy or less. For tumors in sites adjacent to the larynx, priority is given to tumor coverage. In those cases, at a minimum, an attempt will be made to minimize hot spots in the larynx.
  - (c) **Oral Cavity:** Volume receiving more than 50 Gy will be limited; constraints are similar to those noted above for larynx.
  - (d) **Spinal Cord:** No segment of the spinal cord should receive more than 46 Gy. The expanded spinal cord should be limited to 56 Gy for small volume.
  - (e) **Mandible:** Dose to any point should be less than 70 Gy.
  - (f) **Inner Ear:** Mean dose should be less than 34 Gy, and the maximum dose less than 47 Gy.

**Note:** In cases with a conflict/overlap between target and normal tissue, target dose considerations should take priority, at the discretion of the treating physician. An exception to this is the spinal cord dose limitations, which takes priority.

- **Treatment Breaks:** There are no planned treatment breaks on this study; any breaks in planned radiotherapy are strongly discouraged. The Radiation Oncology Study Chair, [name], will be contacted at [contact] for interruptions greater than three treatment days. Radiotherapy interruptions will be permitted for unavoidable mechanical malfunction or serious illness requiring hospitalization, such as sepsis, delirium, severe respiratory compromise or hemodynamic instability, at the discretion of the treating physician and Radiation Oncology Chair. Treatment breaks should be as short as possible. The reason for any interruption in treatment must be documented in the treatment chart.
- **Simulation:** At the time of radiation simulation all patients will have a thermoplastic mask fitted for immobilization. This mask will extend from the top of the skull to below the mid clavicle. Bite blocks, dental rolls and other set-up techniques may be used at the discretion of the treating radiation oncologist.
- **Quality Assurance:**

Prior to the first radiation treatment, the standard quality assurance procedures will be followed. The monitor units required to deliver the prescribed dose shall be calculated. The monitor units generated by the IMRT planning system must be independently checked prior to the patient's first treatment. Measurements in a quality assurance phantom will be done for each patient that will be treated. In addition, film measurements will be taken during the QA period.

On the first day of treatment each patient will have electronic portal images taken, which will be approved by a radiation oncologist prior to delivery of the first treatment, per standard practice.

Weekly Verification portal images will be taken at least once per week and approved by a radiation

oncologist prior to continuation of treatment per standard practice.

- **Isodose Distribution:** All plans will have complete documentation in the patient's chart, including representative CT slices with treatment isodoses. A DVH with all relevant PTV and CTV structures and all normal tissue structures will be generated for each patient and documented in the patient's radiotherapy chart.
- **Treatment Equipment and Delivery:** Treatment will be delivered on the Dana-Farber Varian Clinac 2100EX or Varian TX. 6 MV energy and dynamic multi-leaf collimators will be used to deliver all treatment.

## 5.10 General Concomitant Medication and Supportive Care Guidelines

All medications (excluding prior chemotherapy and biologic, immunologic or radiation therapy) taken within 4 weeks prior to the administration of BKM120 and all concomitant therapy administration during the study with reasons for therapy should be recorded. All prior chemotherapy; biologic, immunologic or radiation therapy; and surgery within 4 weeks prior to the administration of study drug, will be recorded.

Patients on chronic medications that can be given concomitantly with BKM120 should be maintained on the same dose and dose schedule throughout the study period, as medically feasible. The investigator should instruct the patient to notify the study site about any new medications he/she takes after the start of the study drug. All medications (other than study drug) and significant non-drug therapies (including herbal medicines, physical therapy and blood transfusions) administered after the patient starts treatment with study drug, and any changes in dosing should be recorded.

In general, the use of any concomitant medication/therapies deemed necessary for the care of the patient is permitted with the exceptions described in Appendix B.

## 5.11 Duration of Therapy

BKM120 will start **2 weeks** prior to first dose of cisplatin and radiation. BMK120+CRT will then last for 7 weeks. Radiotherapy will be standard of care.

## 5.12 Visit schedule and assessments (see section 10 for schedule and study calendar)

### 5.12.1 Laboratory evaluations

#### 5.12.1.1 Pregnancy Test

A serum pregnancy test ( $\beta$ -HCG) is required for all women of child-bearing potential at screening, within 72 hours prior to the first dose of BKM120. Note: Postmenopausal women must have been amenorrheic for  $\geq 12$  months in order to be considered "of non-childbearing potential". This should be documented appropriately in the patient's medical history. Additional pregnancy tests should be performed as clinically indicated.

#### 5.12.1.2 Hematology

Hematology includes the following parameters: complete blood count (CBC) consisting of red blood cell (RBCs), a total white blood cell count (WBC) with differential (total neutrophil count including bands, lymphocyte, monocyte, eosinophil, and basophil counts); hemoglobin (Hgb); and platelet count.

#### 5.12.1.3 Coagulation Profile

The coagulation profile includes prothrombin time or INR, and activated partial thromboplastin time.

#### 5.12.1.4 Serum chemistry

Biochemistry includes the following parameters: K+, Na+, Ca++, Mg++, LDH, ALT, AST, total bilirubin (direct and indirect), creatinine, amylase, GGT, lipase, alkaline phosphatase (fractionated if alkaline phosphatase is grade 2 or higher), bicarbonate, phosphorus, uric acid, total cholesterol, HDL, LDL, triglycerides, glucose, urea or BUN, albumin, and total protein are required at baseline and at end of treatment. Subsequent assessments always include K+, Na+, Ca++, ALT, AST, total bilirubin (direct and indirect), creatinine, alkaline phosphatase, bicarbonate, phosphorus, glucose, urea or BUN, albumin, and total protein BUT, lipase, total cholesterol, HDL, LDL, triglycerides should be obtained.

Because accurate serum glucose and lipid measurements are required, patients should be fasting at the time of the blood sampling.

#### 5.12.1.5 Urinalysis

Urinalysis includes macroscopic (protein, glucose, ketones, blood, and specific gravity) and will be performed at screening visit and EOT visit. A microscopic (WBC/HPF, RBC/HPF, and any additional findings) exam need only be performed if the urinalysis result is abnormal. This must be supplemented with laboratory quantification of any potentially relevant abnormalities.

#### 5.12.2 Vital signs

Vital sign assessment consists of height (first visit), pulse, blood pressure, respiration rate, temperature and weight. Blood pressure, pulse and respiration rate should be measured on patients after at least 3 minutes in the sitting position as per the visit schedule.

#### 5.12.3 Physical examination

Physical examination will be performed which must comprise a total body examination (general appearance, skin, neck, including thyroid, eyes, ears, nose, throat, lungs, heart, abdomen, back, lymph nodes, extremities and basic nervous system).

Significant findings made after the start of study drug which meet the definition of an Adverse Event must be recorded.

#### 5.12.4 Neuropsychiatric assessments

Patient self-rating mood questionnaires for anxiety and depression (PHQ-9, GAD-7).

Additional assessments may be done according to the clinical judgment of the Investigator. Symptomatic patients ( $\geq$  CTCAE grade 1) must continue with questionnaires on a weekly basis while active on the treatment portion of the study. Instructions on how to instruct the patient to complete the questionnaires as well as how to determine the scores will be provided together with each instrument.

#### 5.12.5 ECG/ECHO

A standard 12 lead ECG is to be performed at screening and as clinically indicated.

An echocardiogram (ECHO) or MUGA will be performed to assess eligibility.

#### 5.12.6 Dental Evaluation

All subjects must undergo dental evaluation prior to beginning BKM120 CRT. Any dental extractions must be performed to allow for enough time for healing of the extraction sockets, which is typically 7-10 days.

#### 5.12.7 Performance status

ECOG performance status (Appendix A).

#### 5.12.8 Efficacy assessments

Time to progression is measured from date of study entry to first progression, otherwise patients are censored at date last known progression-free.

Overall survival is measured from date of study entry to death. Otherwise patients are censored at date last known alive.

[http://ctep.cancer.gov/protocolDevelopment/docs/Recist\\_Guideline.pdf](http://ctep.cancer.gov/protocolDevelopment/docs/Recist_Guideline.pdf)

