### **1.3 Secondary Objectives**

Assess:

- Overall response rate
- Time to progression
- Survival
- Mood alteration from BKM120
- Activity of BKM120 as single agent in sequential biopsies

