 Serum chemistry - K+, Na+, Ca++, Mg++, LDH, ALT, AST, total bilirubin (direct and indirect), creatinine, amylase, GGT, lipase, alkaline phosphatase (fractionated if alkaline phosphatase is grade 2 or higher), bicarbonate, phosphorus, uric acid, total cholesterol, HDL, LDL, triglycerides, glucose, urea or BUN, albumin, and total protein are required at baseline and at end of treatment. Subsequent assessments always include K+, Na+, Mg++, Ca++, ALT, AST, total bilirubin (direct and indirect), creatinine, alkaline phosphatase, bicarbonate, phosphorus, glucose, urea or BUN, albumin, and total protein BUT, lipase, total cholesterol, HDL, LDL, triglycerides should be obtained on Day 1 of CRT and EOT  Coagulation - PT or INR, PTT: Day 1 of CRT and EOT

 Patients must be fasting overnight for at least 8 hours. Additional measurements may be performed as clinically indicated.

 Patients will be assessed weekly for adverse events for the duration of the treatment (2 weeks of BKM120 and 7 weeks of BKM120+CRT = 9 weeks) and every 2 weeks after conclusion of BKM120+CRT (EOT) during the first month, then monthly for 3 months, then every 3 months, until first progression, death, or 2 years post study entry whichever occurs first.

 Follow up (FU) will take place every 2 weeks after conclusion of BKM120+CRT (EOT) during the first month, then monthly for 3 months, then every 3 months, until first progression, death, or 2 years post study entry whichever occurs first. Follow up visits must occur within +/- 14 days of the protocol specified date.

 After first progression, patients will be followed for survival every 3 months until 2 years post study entry.

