## 13. STATISTICAL CONSIDERATIONS

This trial follows a standard 3+3 phase I design. The primary endpoint is to determine the MTD. Patients will be started at a given dose and escalated according to the information outlined in section 5.3. The table below gives the probabilities of the dose escalation scheme outlined in section 5.3.

True Rate of DLT	Probability of Escalation
20%	.71
30%	.49
40%	.31
50%	.17
60%	.08

For example, if the true rate of DLT is 20% at a given dose, there is a 71% probability of escalating to a higher dose.

At most, 46 patients are estimated to be accrued. This is based on studying 6 levels of BKM120+Cisplatin (section 5.3) with at most 6 patients per level plus an additional 10 at the MTD (these 10 accrued to ensure that the adverse event rate at the MTD is acceptable). The estimation of adverse events will be based on studying these 10 additional patients. The width of the 90% confidence interval for the estimation of the adverse event rate will be no more than 56%. The monthly accrual rate is estimated to be 2 to 3 patients.

For secondary objectives: best overall response rate will be summarized as a proportion with a corresponding 90% exact confidence interval, the distributions of progression and survival will be estimated using a Kaplan-Meier method with corresponding 90% confidence intervals for the median or time-specific event time, scores from the GAD-7 and the PHQ-9 to assess mood will be summarized across the timepoints of assessment. Several correlative studies are planned to learn more about how BKM120 blocks PIK. NexGen sequencing of the specimens and studies to investigate the influence of the NFE2L2/KEAP1/CUL3 are planned (see sections 9.1 and Appendix D). Given the small sample size of this trial, these studies are exploratory.

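### Time to progression censors deaths without progression and uses Kaplan-Meier, so the curve overstates actual progression and also looks better than progression-free survival, which is not planned (minor)

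*Combined protocol and SAP*

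**What the plan says.** Section 1.3 lists "Time to progression" and survival as separate secondary objectives. Section 5.12.8 defines the first as follows: "Time to progression is measured from date of study entry to first progression, otherwise patients are censored at date last known progression-free". The event is progression alone. Death is not named in this definition, but a patient who dies without progression falls under the residual clause and is censored.

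Death is an event only in the other time-to-event endpoint: "Overall survival is measured from date of study entry to death. Otherwise patients are censored at date last known alive".

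Section 13 says that "the distributions of progression and survival will be estimated using a Kaplan-Meier method", "with corresponding 90% confidence intervals for the median or time-specific event time". It gives no landmark time, no hypothesis and no threshold for progression.

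The footnotes to the visit schedule (section 10, Table 17) continue follow-up "until first progression, death, or 2 years post study entry whichever occurs first". For progressed patients they add: "After first progression, patients will be followed for survival every 3 months until 2 years post study entry". Death before progression is thus foreseen as one way in which follow-up ends. Nothing in the documents defines progression-free survival or names a competing-risk estimator.

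**The concern.** A patient who has died cannot progress. Kaplan-Meier treats a censored patient as still at risk after the censoring date, with the same future as those who remain under observation. For someone still alive at the 2-year limit that is a reasonable convention. For someone who has died it describes a world in which the death did not happen.

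Two misreadings follow, in opposite directions. One minus the curve, taken as the share of patients who progress, is too high. The curve itself, taken as the share alive and free of progression, is also too high, because patients who died without progressing are not counted as failures. The plan offers no second endpoint that would show which reading is meant.

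At stake is the interpretation of a descriptive efficacy figure from a single-arm trial. The rationale in section 2.3 rests on overcoming radioresistance in patients at high risk of loco-regional recurrence, so progression is the endpoint closest to it.

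**Working it through.** **Plan's own figures.** The plan states no expected progression or death rate, so there is no figure of its own to reproduce on this point. The one stated number used below is the maximum sample size: "At most, 46 patients are estimated to be accrued". It checks: 6 levels × 6 patients + 10 = 46.

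**Direction.** At each progression time, let d be the number progressing and n the number at risk.
- One minus Kaplan-Meier rises by KM(t−) × d/n, where KM falls only at progressions.
- The Aalen-Johansen cumulative incidence rises by S(t−) × d/n, where S falls at progressions and at deaths without progression.
- S never exceeds KM, and is smaller after the first such death. Every later progression then adds more to one minus Kaplan-Meier than to the cumulative incidence. If no progression follows a death, the two agree.

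**Size.** The rates are assumptions. The only outcome anchor in the documents is a historical cure rate of around 50% (section 2.1), which suggests looking at 30-50% progression at 2 years. Death without progression is varied from 5% to 20%. Cause-specific hazards are taken as constant.

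*Version A: fix the actual 2-year proportions*, c progressing and d dying first. Total hazard over 2 years H = −ln(1 − c − d); progression part h = H × c/(c + d); one minus Kaplan-Meier = 1 − exp(−h); progression-free survival (PFS) = 1 − c − d.

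Example, c = 40% and d = 15%: H = −ln(0.45) = 0.799; h = 0.799 × 0.40/0.55 = 0.581; one minus Kaplan-Meier = 1 − exp(−0.581) = 44.1%.

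| c | d | 1 − KM | Over c by (points) | KM | PFS | KM over PFS by (points) |
|---|---|---|---|---|---|---|
| 30% | 5% | 30.9% | 0.9 | 69.1% | 65% | 4.1 |
| 30% | 20% | 34.0% | 4.0 | 66.0% | 50% | 16.0 |
| 40% | 15% | 44.1% | 4.1 | 55.9% | 45% | 10.9 |
| 50% | 5% | 51.6% | 1.6 | 48.4% | 45% | 3.4 |
| 50% | 20% | 57.7% | 7.7 | 42.3% | 30% | 12.3 |

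*Version B: fix the Kaplan-Meier progression F* and the net risk of death without progression D (the risk if nobody progressed). With a = −ln(1 − F) and b = −ln(1 − D), cumulative incidence = a/(a + b) × (1 − exp(−(a + b))) and PFS = (1 − F)(1 − D).

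| F = 1 − KM | Cumulative incidence at D = 5 / 10 / 20% | Overstatement (points) | PFS | KM over PFS by (points) |
|---|---|---|---|---|
| 30% | 29.3 / 28.6 / 27.1% | 0.7 / 1.4 / 2.9 | 66.5 / 63.0 / 56.0% | 3.5 / 7.0 / 14.0 |
| 40% | 39.1 / 38.1 / 36.2% | 0.9 / 1.9 / 3.8 | 57.0 / 54.0 / 48.0% | 3.0 / 6.0 / 12.0 |
| 50% | 48.9 / 47.7 / 45.4% | 1.1 / 2.3 / 4.6 | 47.5 / 45.0 / 40.0% | 2.5 / 5.0 / 10.0 |

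Simulating the 40% row with 46 patients gave a mean one minus Kaplan-Meier of about 40%, against a mean Aalen-Johansen estimate of 38.9%, 38.1% and 36.4%, in line with the formulas.

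**Against the precision available.** An approximate 90% half-width at 40% progression is 1.645 × √(0.4 × 0.6/46) = 11.9 points with all 46 patients, and 1.645 × √(0.4 × 0.6/10) = 25.5 points with the 10 expansion patients alone. Loss to follow-up would widen both.

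**The case against.** The best defence is that this is a choice of endpoint. Time to progression with deaths censored is a recognised endpoint, and the plan names and defines it consistently. A reader might infer that the estimate is simply biased. That holds only if the target is the actual probability of progression, and the plan does not say so. What stands against the plan is narrower: it states neither its target nor the independence assumption needed to read the curve as progression without death.

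A reader might also infer that treatment-related deaths drop out of the trial's results. They do not. Overall survival counts deaths as events (section 5.12.8), death is a serious adverse event (5.12.12), deaths during treatment or within 30 days must be reported (5.12.13), and the monitoring committee's material may include them (12.2). They are absent as events only from this endpoint.

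Nor does the plan commit to a 2-year progression figure or a historical comparison. Two years is the follow-up limit, used here as a convenient time for the arithmetic. If an outside figure also censored deaths, the planned method would be the like-for-like one.

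On size, the objection is largely right. The death rate is wholly assumed. The 8-point extreme needs only 30% of patients alive and progression-free at 2 years, which fits poorly with a cure rate near 50%. The usual shift is well inside the sampling error, and pooling would mix up to six dose levels. The 3-16 point gap is a difference between two endpoints: it measures a possible misreading, not an error in estimating time to progression.

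Even so, a wide confidence interval shows imprecision and does not show this shift, and nothing is lost by removing the ambiguity.

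**Conclusion.** The point holds as a minor one. As written, the progression curve answers a hypothetical question that the plan does not state, overstates actual progression once a death without progression precedes a later progression, and lies above the fraction alive and progression-free.

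Under constant hazards, with 30-50% progression and 5-20% death without progression at 2 years, the overstatement is about 1-5 points. It reaches about 8 only when the assumed rates are actual proportions at the top of both ranges. The distance to progression-free survival is about 3-16 points. Both depend on assumed death rates; if few patients die first, both become negligible.

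The endpoint is secondary and descriptive, with no test or decision rule. The MTD, the sample size of at most 46, the safety reporting and the overall survival analysis are unaffected.

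**What to change.** In sections 5.12.8 and 13:

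1. Estimate progression by cumulative incidence (Aalen-Johansen), with death without progression as a competing event and 90% confidence intervals.
2. Add progression-free survival, with progression or death from any cause as the event, by Kaplan-Meier with 90% confidence intervals.
3. If the Kaplan-Meier time to progression is kept, label it as censoring deaths without progression, so that it is read neither as the share who progress nor as the share alive and progression-free.

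The cost is a few lines of text and a little analysis in standard software. Progression and death dates are already collected up to 2 years under Table 17, so no visit, data item or patient is added.
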